## **A. SPECIFIC AIMS**

- 1. Aim 1. Determine the effects of a 4-week course of anti-inflammatory supplementation (PolyResveratrol-SR®) on vascular function, subclinical atherosclerosis and CV biomarkers**
- 2. Aim 2. Define adherence and barriers to compliance to supplementation.**

## **B. BACKGROUND AND SIGNIFICANCE**

Adverse pregnancy outcomes (APOs) occur in up to 20% of all pregnancies and are associated with a lifetime of higher cardiovascular disease (CVD) risk. **Aberrant and persistent systemic inflammation is a hallmark of both APOs and CVD.** An inappropriate uterine innate immune response to invading fetal cytotrophoblasts is thought to underlie poor placentation and vascular-related APOs; inflammation of the uterine cavity evokes contractions and contributes to preterm birth. Levels of cytokines involved in endothelial inflammation, an instigating event in hypertensive and atherosclerotic processes, were higher in the 2nd trimester in women destined to have APOs. Women with a past APO have higher levels of systemic inflammation, including c-reactive protein and interleukin-6 (IL-6), in the years after delivery versus women with no APOs. A similar pro-inflammatory cytokine profile has been observed in patients with overt CVD. **Intervening on systemic inflammation may be a viable strategy to interrupt the progression from APO to CVD.**

Dietary supplements, such as polyphenols, are anti-inflammatory and inhibit vascular inflammation with potentially few barriers to adherence. **Given the hypothesized contribution of a persistent pro-inflammatory state to the excess CVD risk observed in women after APO, utilization of a polyphenol dietary supplement to specifically target inflammation holds promise as a low-burden intervention to prevent or delay APO-related CVD.** To our knowledge, efficacy and tolerability of a dietary polyphenol supplement has not been investigated in women with a history of APO. To fill in this critical gap in knowledge, we propose to test the vascular function and CV biomarker, i.e., IL-6, IL-10, intracellular and vascular cell adhesion molecule-1 (ICAM-1 and VCAM-1), responses to a 4-week anti-inflammatory dietary supplementation in a clinical trial pilot study of 56 women, 28 assigned to the intervention and 28 to the control group, in the first 3 years after an APO.

## **C. PRELIMINARY STUDIES**

Other studies of endothelial dysfunction and APOs have consistently shown that women who go on to have APOs have evidence of endothelial dysfunction that is detectable in the 1st trimester of pregnancy. In a recent paper, we demonstrated that there was no difference in evidence of pre-pregnancy endothelial dysfunction between women who did and did not go on to have a preterm or small for gestational age delivery ~3 years later (OR: 1.01, 95% CI: 0.74, 1.39). **Our results suggest that the endothelial dysfunction that contributes to APOs (and eventual CVD) may not develop until pregnancy begins**, highlighting the importance of the pregnancy period for influencing the CVD risk trajectory in women. In this investigation, only black race was associated with greater risk of preterm birth and/or small for gestational age delivery, even after adjustment for relevant covariates

**Higher BMI and central BP in women with a past APO.** In early data from an ongoing study conducted in the PI's lab, we found a trend towards higher central systolic BP in women with a past APO (*Table, unpublished data*). Findings suggest that differences in sensitive measures of vascular function are detectable soon after an APO but before overt CVD.

	APO+ n=17	APO- n=36
Age (yrs)	33	33
Race (% AA)*	28	17
aSBP (mmHg)*	102	97
bSBP(mmHg)	113	109
BMI (kg/m  )*	29.2	26.0

**Table Legend.** AA: African American; aSBP: aortic systolic BP; bSBP: brachial systolic BP

#### **D. RESEARCH DESIGN AND METHODS AND DATA ANALYSIS**

**Research Design.** We will invite 56 women with an APO within the past 3 yrs to participate. Women will be randomly assigned to the 4-wk intervention group (n=28) or a standard care group (n=28) using a computerized random number generator, stratified by race. Assuming up to 25% with poor adherence, we expect that 42 women (21 each arm) will complete the study. No data exists related to effects of supplementation on vascular function in our population, we assumed a medium effect size, i.e. Cohen's  $d \sim 0.50$  and accepting a  $\beta=0.80$ , to generate sample sizes. Generation of effect sizes is a key outcome of this study. We will conduct a vascular assessment and blood draw at two visits: before the intervention begins and within 3 days of completing the intervention. We will conduct visits during the early follicular phase of menstrual cycle to account for fluctuating hormones. Vascular testing will be performed in the supine position and  $\geq 4$  hours after a light meal. Surveys for Aim 2 will be completed within the first 2 weeks of study enrollment, and interviews for Aim 2 will be conducted within 1 week of Visit 2, in-person or via telephone.

**Anti-inflammatory supplementation intervention.** Participants randomized to the supplementation intervention will receive PolyResveratrol-SR® (100 mg curcumin phytosome, 100 mg quercetin phytosome, 100 mg green tea phytosome, 100 mg trans-resveratrol, 100 mg trans-pterostilbene; Thorne Research). Participants will be asked to take 2 doses/day (1g total). Participants randomized to supplementation will receive a daily email reminding them to take the supplement. **Covariates.** Medical history, age, and sociodemographics will be obtained via self-report. We will use validated surveys to determine physical activity, sedentary behavior, and smoking history. Height and weight will be measured.

**Aim 1 Outcomes.** The outcomes will be measured in-person. All outcomes are listed and described below. [name] has extensive experience collecting the measurements described below.

1. **Blood pressure.** Resting brachial systolic BP (SBP) and diastolic BP (DBP) will be measured using an automated oscillometric cuff (HEM-907 XL; Omron, Shimane, Japan) after 10 min of supine rest in a quiet, dimly lit room. Brachial BP will be obtained in duplicate with 1 min between the first and second reading. If the two values are not within 5 mmHg of each other, another measurement was taken until two consecutive values within 5 mmHg of each other are obtained. These two values will be averaged and used for analysis.
2. **Arterial stiffness.** Participants will remain supine in a quiet room. The aortic waveform will be reconstructed from radial artery pressure waveforms obtained from a 10-s epoch

using applanation tonometry (Millar Instruments, Houston, TX) and calibrated with brachial MAP and diastolic BP with a generalized validated transfer function (SphygmoCor; AtCor Medical, Sydney, Australia). From this central waveform, we will derive central BP, augmentation index (AIx), and end-systolic pressure. An in-device quality rating of  $\geq 80\%$  will be required for all recordings used in analysis. We will measure central (aortic) pulse wave velocities in the supine position using gold-standard techniques. We will measure distances from the suprasternal notch to the femoral artery and from the carotid artery to the suprasternal notch with a tape measure, recorded to the nearest mm. The distance from the carotid site to the suprasternal notch will be subtracted from the distance between the suprasternal notch and femoral artery to account for the divergent directions of pulse wave propagation. We will use the same high-fidelity strain-gauge transducer to obtain pressure waveforms at the right common carotid artery and then at the right femoral artery for central pulse wave velocity. Pulse wave velocity will be calculated as distance/time, using the distances between measurement points and the measured time delay between 10 proximal and distal waveforms (SphygmaCor; AtCor Medical). ECG will be recorded simultaneously, and the peak of the R wave will be our timing marker. BP influences pulse wave velocity, so we will also adjust pulse wave velocity for aortic MAP.

3. *Resting forearm blood flow*. Forearm blood flow (FBF) will be measured using strain gauge plethysmography (EC-4; Hokanson, Inc., Bellevue, WA). A standard BP cuff will be positioned around the upper arm. An appropriately sized strain gauge will be placed around the widest part of the forearm, and a pediatric cuff placed around the wrist to occlude hand blood flow. Before measuring FBF, the wrist cuff will be inflated to 250 mm Hg of pressure for 1 minute. FBF will be determined by inflating the upper cuff to 50 mm Hg (to oppose venous backflow) for 7 s and then deflating it for 8 s. An average of six of these 15-s plethysmographic cycles will be used to determine FBF, expressed as milliliters per minute per 100 mL of forearm tissue and as flow per unit pressure, e.g. conductance, using the equation:  $conductance = (FBF/MAP) \times 1000$ .
4. *Vascular endothelial function*. Reactive hyperemia, e.g. resistance vessel endothelial function, will be measured immediately after FBF. Arm blood flow will be occluded by inflating the upper arm BP cuff to 250 mm Hg for 5 min. One minute prior to the release of the upper arm cuff, the wrist cuff will also be inflated to 250 mm Hg. The upper arm cuff pressure will be rapidly released and changes in forearm volume will be recorded via the strain gauge, in 15-s cycles as described above, for 3 min (13 readings). The highest reading will represent peak blood flow. All 13 measurements will be plotted against time, and the area under this curve will represent total reactive hyperemia. We chose to measure reactive hyperemia rather than flow-mediated dilation due to the high intra- and interobserver variability in flow-mediated dilation measurements.
5. *Carotid intima-media thickness*. The right common carotid artery will be imaged with ultrasound (Logiq GE S8) using a 12-MHz linear array probe. Intima-medial thickness will be defined as the distance between the leading edge of the lumen–intima border and the leading edge of the media–adventitia border on the far wall of the artery. We will average a 5mm segment obtained approximately 20 mm proximal to the carotid bifurcation for analysis.
6. *Blood analyses*. We will collect 30 mL(2 Tb) of blood into an EDTA containing tube and serum tube using venipuncture and a butterfly needle. Blood will be centrifuged at 1300 g for 10 min, aliquoted into 0.25 mL cryotubes, and stored at -80°C until analysis. We will determine levels of circulating IL-6, IL-10, ICAM-1, and VCAM-1 using commercially available ELISA kits (R&D Systems). We will bank unusedl blood for future, as yet undetermined analyses. Participants will be informed of this intent before providing blood. Blood will be labelled and linked to clinical data and demographics using a

unique identifier; samples will be de-identified for storage at the PHRC and for future analyses.

7. **Covariates: Medical and Pregnancy History and Demographics.** We will ask questions about demographic, medical, and pregnancy history. Answering questions will not provide identifiable information, **Self-reported activity:** We will use validated surveys to quantify physical activity and sedentary behavior, **Diet History.** We will use a validated survey to assess diet composition in the previous 6 months.

**Data Analyses.** We will calculate the 25th and 75th percentile for each biomarker and vascular function test and use these values as cut-offs for “low” and “high” levels, respectively. We will test for differences in biomarker levels between women by APO status and race using a t-test or Mann-Whitney U test, depending on the distribution of the variables. We will use separate multiple linear regression models to determine associations of each exposure (continuous levels of biomarkers; quartiles; and high or low levels of these biomarkers) with continuous measures of our outcomes (individual indices of vascular function, e.g. BP, arterial stiffness, augmentation index, FBF, endothelial function, and intima-media thickness) in all 56 women. We will use logistic regression to test for associations between continuous and categorical levels of biomarkers with categorical outcomes: the likelihood of having hypertension or prehypertension, high central arterial stiffness, low endothelial function, and high carotid intima-media thickness in all 56 women. We will test for unadjusted associations and then adjust all regression analyses for key co-variables: maternal age, race, and smoking. We will test for associations after furthering adjusting for years of education, body mass index (BMI), parity, and physical activity, in the index pregnancy in exploratory analyses. We will test for an interactive effect of APO status and race on these associations using a multiplicative interaction term in separate analyses and conduct all analyses stratified by APO status and/or race if the interaction is significant. We will conduct a sensitivity analysis by repeating our statistical tests only in the primiparous women as prior pregnancy is associated with lasting changes in vascular function and may influence our outcome and exposure variables.

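### The stated inputs (d of about 0.50, 80% power) do not give 28 per arm: a conventional two-arm test has 45% power at 28 and 35% at 21

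*Combined protocol and SAP*

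**What the plan says.** The sample-size basis is in the Research Design paragraph of Section D. On allocation it says "Women will be randomly assigned to the 4-wk intervention group (n=28) or a standard care group (n=28"); Section B gives the same numbers ("28 assigned to the intervention and 28 to the control group"). On retention: "Assuming up to 25% with poor adherence, we expect that 42 women (21 each arm) will complete the study".

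On the effect size: "No data exists related to effects of supplementation on vascular function in our population, we assumed a medium effect size". The figure is a Cohen's d of about 0.50, and with β = 0.80 it was used "to generate sample sizes". The next sentence adds a second purpose: "Generation of effect sizes is a key outcome of this study".

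The plan does not give the test, alpha, sidedness, the endpoint to which d applies, the SD that standardises it (raw, change or baseline-adjusted) or the pre-post correlation. The Data Analyses paragraph of Section D does not supply them. Its t-test or Mann-Whitney comparison is by APO status and race, and its models relate biomarkers to vascular measures ("We will use separate multiple linear regression models to determine associations of each exposure"). Neither compares supplement with standard care.

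**The concern.** The text presents 56 women as the product of a calculation from d and power, so the calculation should be reproducible. For the obvious comparison, two parallel arms at conventional alpha, these inputs call for more than twice 28 per arm.

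The notation is also wrong. β is the type II error rate, so β = 0.80 read literally is 20% power. The intended meaning is almost certainly power of 0.80, β = 0.20.

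The risk is in interpretation. A reader may take the trial as 80% powered for a medium between-arm effect and read a null result as evidence against one. Effect sizes from this trial are also a key outcome, and the plan does not say how imprecise they will be.

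**Working it through.** **Inputs from Section D.** d = 0.50; power 0.80 (written as β); 28 per arm randomised; 21 per arm completing. The retention sum is right: 28 × 0.75 = 21. Because the allowance is up to 25%, 21 is the worst case.

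**Assumed, because not stated.** Two-sample t-test with alpha two-sided 0.05; alternatives follow.

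**1. Trying to reproduce 28 per arm.** The normal approximation gives n per arm = 2(z₀.₉₇₅ + z₀.₈₀)²/d² = 2(1.960 + 0.842)²/0.25 ≈ 62.8, so 63. The exact noncentral-t calculation gives 64 (power 0.801; 63 gives 0.795). Allowing 25% loss, 64/0.75 ≈ 85.3, so 86 per arm randomised. The plan's 28 is not reproduced. Read literally, 20% power needs only 11 per arm, which does not match either.

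**2. Power at the planned sizes.** Noncentrality δ = d√(n/2), with 2n − 2 degrees of freedom.

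- n = 28: δ = 0.5√14 = 1.871, critical t = 2.005, power 0.451.
- n = 21: δ = 0.5√10.5 = 1.620, critical t = 2.021, power 0.353.

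**3. Other between-arm tests at d = 0.50.**

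| Test | Per arm for 80% | Power at 28 | Power at 21 |
|---|---|---|---|
| t-test, two-sided 0.05 | 64 | 45% | 35% |
| t-test, one-sided 0.05 | 51 | 58% | 48% |
| t-test, one-sided 0.20 | 23 | 85% | 78% |

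To reach 80% with the t-test, two-sided alpha would have to be 0.30 at 28 per arm or 0.42 at 21.

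**4. Baseline adjustment.** If d is on the raw SD, ANCOVA raises the effective effect to d/√(1 − r²), with 2n − 3 degrees of freedom. The documents give no r, so a range is shown.

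| Pre-post r | Power at 28 | Power at 21 |
|---|---|---|
| 0.3 | 49% | 38% |
| 0.5 | 56% | 45% |
| 0.7 | 73% | 60% |
| 0.8 | 86% | 75% |

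Power of 80% needs r of about 0.76 at 28 per arm and 0.83 at 21. If d is already on the change SD and change is what is compared, the 45% and 35% stand.

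**5. Routes that land near the planned numbers.**

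- *Within-arm paired test, one-sided 0.05:* 27 pairs needed; 82% power at 28 and 71% at 21. It ignores the control arm.
- *Single-predictor regression in all women, f² = 0.15 taken as medium, two-sided 0.05:* N = 55 needed, close to 56. For two equal groups d = 2√f² = 2√0.15 = 0.77, not 0.50. Conversely d = 0.50 gives f² = 0.5²/4 = 0.0625, which needs N = 128.
- *Group-by-time F-test, f = 0.25, two visits:* with λ = 2f²N/(1 − r), 34 women in total are needed at r = 0.5 and 40 at r = 0.4; at 42 completers power is 89% and 82%. For a difference in change of D raw SDs, λ = D²N/[8(1 − r)]. Equating the two gives D = 4f = 1.0 raw SD, twice the stated d. With D = 0.50 and r = 0.5, power returns to 45% at 56 women and 35% at 42.

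**6. What the design can detect and estimate.** For the two-sided 0.05 t-test, the detectable d at 80% power is 0.76 (28 per arm) or 0.89 (21 per arm). The noncentral-t 95% CI around an observed d of 0.5 is −0.03 to 1.03 (28 per arm) or −0.12 to 1.11 (21 per arm), a half-width of about 0.53 or 0.61 SD.

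**The case against.** The strongest reply is that nothing has been miscalculated, because no formula is given. The 45% and 35% rest on a test and alpha supplied from outside the plan, and they ignore a baseline that the trial measures. With a high pre-post correlation, ANCOVA could reach 80%, and a group-by-time F-test with a medium f of 0.25 would plausibly explain 42 completers. The loss figure is also soft. The 25% is for poor adherence, and poorly adherent women could still attend Visit 2. Finally, this is a pilot, estimating effect sizes is a stated goal, and the only decision threshold (Aim 2 adherence) does not depend on d.

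Much of this stands. No particular power can be attributed to the plan, and the working does not show that every design with 28 per arm is underpowered. The consequence is modest.

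The objection does not rescue the statement as written. The plan does not justify 56 by feasibility; it says d and power generated the number. Every route found that reaches 80% at or near the planned size needs an unstated correlation, a lenient alpha, a test that discards the control arm, or a different effect size. The group-by-time route needs an effect twice the stated d. As for 21 per arm, the plan itself treats poor adherence as non-completion ("we expect that 42 women (21 each arm) will complete the study"), and the shortfall is present at the full 28 anyway.

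**Conclusion.** The concern holds. The stated inputs do not give 28 per arm, or 21 completing, for a conventional comparison of the two arms, and the method behind the number cannot be recovered from the text. The size of the gap is 28 against 64 per arm for a two-sided 0.05 t-test at d = 0.50, or against 51 at one-sided 0.05.

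The failure to reproduce 28 under these tests is certain. The specific power figures are conditional on the assumed test and alpha and, for ANCOVA, on the assumed correlation. This should be fixed. Pilot status keeps it from being more serious but does not make the power statement correct.

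**What to change.** Keep 56 women and change the text of Section D.

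1. Write power = 0.80 (β = 0.20).
2. Ask the authors which calculation gave 28 per arm. If there is one, state its test, alpha, sidedness, endpoint, the SD behind d and the pre-post correlation, and have the Data Analyses paragraph name the same test as the between-arm comparison.
3. If there is none, replace the power statement with wording such as:

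> The sample size was chosen for feasibility and to estimate effect sizes. For a two-arm t-test at two-sided 0.05, 28 (21) per arm gives 45% (35%) power for d = 0.5. With baseline adjustment, power is 56% (45%) if the pre-post correlation is 0.5 and 73% (60%) if it is 0.7. Without adjustment, the detectable d at 80% power is 0.76 (0.89). Effect sizes will be reported with 95% confidence intervals, with an expected half-width of about 0.53 to 0.61 SD. A non-significant between-arm result will not be read as no effect.

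This wording presupposes a between-arm comparison, so the Data Analyses paragraph must add one.

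The cost is a few sentences and one query, with no extra participants or procedures. The stated power becomes less favourable.

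### Effect sizes are a key outcome of the pilot, but the plan gives no estimator, standardising SD or confidence interval for them, and no comparison by randomised arm

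*Combined protocol and SAP*

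**What the plan says.** Section B describes a "clinical trial pilot study of 56 women, 28 assigned to the intervention and 28 to the control group". The Research Design paragraph of section D says "No data exists related to effects of supplementation on vascular function in our population", and continues that "we assumed a medium effect size", given as a Cohen's d of about 0.50. On numbers it says "Assuming up to 25% with poor adherence, we expect that 42 women (21 each arm) will complete the study". It then states "Generation of effect sizes is a key outcome of this study". On measurement, "We will conduct a vascular assessment and blood draw at two visits", one before and one shortly after the intervention.

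That is all the plan says about effect sizes. No formula, standardising SD, confidence interval or intended use is given. The Data Analyses paragraph of section D covers percentile cut-offs, biomarker comparisons by APO status and race, and regressions of vascular measures on biomarkers in all 56 women. It does not compare the randomised arms. The Aim 2 analyses cover survey averages, the proportion with adequate adherence, and interviews. No section lists an outcome SD or a correlation between visits as something to be reported.

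**The concern.** A named key outcome should have a defined estimator, and this one has none. With two visits, d could be the difference in Visit 2 means over a single-visit SD, the difference in mean change over the SD of change, or an adjusted difference over either. These give different numbers from the same data.

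A bare d from 21 women per arm is also very imprecise. If it is reported without an interval, readers may take a chance high or low value as information about the supplement. The SD and the visit-to-visit correlation come from the same women, are better determined than d, and are needed to interpret it. They are not listed as outputs.

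**Working it through.** **Inputs from the plan.** 28 randomised and 21 expected completers per arm, d = 0.50, two visits.

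**Inputs assumed.** Two-sided alpha 0.05, because none is stated. The visit-to-visit correlation r is not given, so 0.5, 0.7 and 0.8 are shown.

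**1. The plan's own figures.** 56 × 0.75 = 42, or 21 per arm, so the attrition arithmetic reproduces. The sample size does not follow from d = 0.50 with 80% power in a simple two-group comparison: 2(1.96 + 0.842)² / 0.50² = 15.70 / 0.25 = 62.8, so 63 per arm. That is a separate matter, and nothing below depends on it.

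**2. Unadjusted d.** The standard error at d = 0.50 is √(2/21 + 0.50²/84) = 0.313. Inverting the noncentral t distribution gives these 95% CIs:
- 21 per arm (40 df): -0.12 to 1.11.
- 28 per arm (54 df): -0.03 to 1.03.

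If the true d is 0.50, about 5% of pilots of 21 per arm would observe d at or below zero, 21% below 0.25 and 18% above 0.80.

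**3. Visit 1-adjusted difference, in baseline-SD units.** The half-width is t(39 df) × √[(2/21)(1 − r²)], with t = 2.02. Intervals around 0.50 with 21 per arm:
- r = 0.5: half-width 0.54, interval -0.04 to 1.04.
- r = 0.7: half-width 0.45, interval 0.05 to 0.95.
- r = 0.8: half-width 0.37, interval 0.13 to 0.87.

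These treat the baseline SD as known and the arms as balanced at Visit 1, so they are slightly optimistic.

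**4. Choice of standardiser.** With equal SDs at both visits, the SD of change is SD × √[2(1 − r)]. Using it in place of the single-visit SD multiplies d by 1/√[2(1 − r)]:
- r = 0.5: 1.00.
- r = 0.7: 1/√0.6 = 1.29.
- r = 0.8: 1/√0.4 = 1.58.

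At r = 0.8, the same difference could be reported as d = 0.50 or d = 0.79.

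**5. If d were used to size a later trial (assumed use).** Required n per arm for 80% power is 15.70/d², plus about 1 as a small-sample term that matters only at the small end. With true d = 0.50 and 21 per arm, the 10th and 90th percentiles of the estimate give:
- Unadjusted, d from 0.105 to 0.922: 15.70/0.1049² ≈ 1,430, down to 15.70/0.9225² + 1 = 19.4, so 20. Simulation put the 10th percentile at 0.109, which gives about 1,320; the upper end is therefore best read as 1,300 to 1,400 or so.
- Adjusted, r = 0.7, from 0.304 to 1.135 residual SDs: 15.70/0.304² ≈ 170, down to 15.70/1.135² + 1 = 13.2, so 14.
- Adjusted, r = 0.8, from 0.436 to 1.278 residual SDs: 15.70/0.436² ≈ 83, down to 15.70/1.278² + 1 = 10.6, so 11.

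About 24 to 26% of trials sized on the unadjusted d would have less than 50% true power.

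**6. What the same 42 women say about SD and correlation.**
- Pooled SD, 40 df: 95% limits are 0.82 and 1.28 times the estimate (-18% to +28%). Since n scales with SD², n changes by a factor of 0.67 to 1.64.
- Correlation, Fisher z with standard error 1/√39: 0.23 to 0.70 if r = 0.5, and 0.50 to 0.83 if r = 0.7. Through 1 − r², n changes by a factor of 0.68 to 1.26, or 0.62 to 1.46.

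Each of these 95% ranges moves n about 2.4-fold or less. The 80% range for d moves it about 70-fold unadjusted (1,430/20), 12-fold at r = 0.7 (170/14) and 7.5-fold at r = 0.8 (83/11).

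**The case against.** Four objections have weight.

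*No follow-on trial is mentioned.* This is correct. A reader might infer from the pilot label that the observed d will size the next study, but no section says so. Step 5 is therefore conditional. The missing definition, interval and arm comparison do not depend on it.

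*The wording is looser than a bare d.* The plan calls effect sizes one key outcome, not the only one. The term is undefined and could include mean differences in natural units. Adherence, a feasibility criterion and contact with drop-outs are also planned. This stands, and it is why the point is about lack of definition rather than a wrong choice of d. The 25% loss is also an upper figure, but full retention improves the interval only to -0.03 to 1.03.

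*Baseline adjustment would make the result more precise.* It would, by an amount that depends on r, so the unadjusted range should not be read as the only one. The plan specifies no such adjustment and gives no r. Even at r = 0.8 the half-width of 0.37 is large against 0.50.

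*About half of trials sized on the pilot would be underpowered.* A reader might draw this as the main harm, but it does not measure imprecision. Any roughly unbiased estimate leaves about half of later trials below target power: 50% with a pilot of 21 per arm and still 47% with 1,000 per arm. Only the chance of severe underpowering reflects the small pilot.

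**Conclusion.** The point holds as a gap in definition and reporting. The plan names effect sizes as a key outcome without an estimator, standardiser or interval, and its Aim 1 analysis contains no comparison by randomised arm that could produce them. An unadjusted d of 0.50 would carry a 95% CI of roughly ±0.6, and the choice of standardiser alone could change d by 29% to 58% at correlations of 0.7 to 0.8.

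The correlation values and the two-sided 5% level are assumptions; the documents give neither. Use of d to size a later trial is also an assumption. Under it, the observed d alone would be a poor basis, with or without baseline adjustment.

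A reader might also conclude that the pilot estimates the SD and correlation well. The figures support only that they are better determined than d: a correlation of 0.5 has limits of 0.23 and 0.70, so both need their own intervals. Nothing here makes the pilot invalid.

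**What to change.** Define the effect size in the Research Design paragraph of section D, and add an analysis by randomised arm to the Data Analyses paragraph. Suggested text:

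*For each Aim 1 outcome, the effect estimate is the difference between randomised arms at Visit 2, adjusted for the Visit 1 value, in natural units with a 95% confidence interval. It will be reported with the Visit 1 SD and the correlation between Visit 1 and Visit 2 (or the residual SD), each with a confidence interval, and with attrition by arm. If a standardised effect is quoted, it will be divided by the pooled Visit 1 SD and given with its confidence interval. No later trial will be sized on the observed standardised effect alone.*

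Changing only the Research Design sentence would leave the key outcome without an analysis, so both places need the edit. If a later trial is intended, the plan should say so. Its target difference would then need separate justification, because the documents give no clinically relevant difference for any outcome.

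The cost is wording and a few more rows in the results table, all from data already being collected, with no extra participants, visits or measurements. The downside is that there is no single headline effect size.
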